- 2. Video-Perceptual Analysis.** Videostroboscopic clips will be collected during clinical visits to the NYU Voice Center per normal protocol. Briefly, following application (spray) of topical oxymetazoline and 4% lidocaine, a flexible endoscope will be passed through the nasal cavity and into the pharynx. Subjects will be asked to perform a variety of vocal tasks, including sustained phonation, rapid phonation, sniffing, and counting. Each exam will be recorded as is routine in our practice. There will be a total of three videos collected from each subjects (initial, interval, and final). The images/video obtained will be used for two separate analyses, as described below. For the expert analysis of the videostroboscopy, the clips will be edited in a manner that allows for de-identification and shortening of the clips to demonstrate the most salient parts of the video, including clear imaging of the pathology and at least 5 seconds of continuous mucosal wave. The edited clips will then be sent to 6 expert reviewers (otolaryngologists with a strong laryngology background) for review. The clips will be paired as follows: initial with interval and interval with final. The videos will be presented in random order, followed by a rating form. On the rating form, the reviewers will be asked to rate change in both mucosal wave and glottal closure on a relative 3-point scale (worse, same, better), as described in our previous work.(30) The reviewers will then be asked to return the rating forms, so the data can be collated. Twenty (20) percent of the samples will be repeated randomly for both the expert reviewer and lesion measurement analyses to assess intra-rater reliability. Data will also be subjected to analysis of inter-rater agreement.

The second analysis will be to measure lesion size. This method has been previously described by our group.(30) Briefly, still images of the glottis will be obtained from the video such that the vocal folds are captured in an open position (at least 40 degrees at the anterior commissure). Image J software (NIH) will then be used to outline the lesion and measure the length of the ipsilateral vocal fold (as shown in **Figure 4**). The ratio of these will be used as the adjusted size variable. Measurements will be done bilaterally when appropriate.

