Presence of phonotraumatic lesion deemed to be etiologic for the complaint of dysphonia	Known allergy or hypersensitivity to oral steroids
Voice therapy deemed to be the primary (or at least initial) treatment to address the dysphonia	Active infection
Willingness to be an active participant in voice therapy	Diabetes Mellitus
	Prior history of radiation to the neck
	Recent myocardial infarction
	Recent gastrointestinal surgery with bowel anastomosis (3 months)
	Active peptic ulcer
	Pregnancy
	Severe depression or history of psychosis
	History of recent laryngeal surgery (within 12 months)
Figure 1. Inclusion and exclusion criteria for the proposed trial.	

Figure 2

[figure not shown]

Figure 3

Dependent Variable	Brief Description
VHI (primary dependent variable)	The change in VHI-10 scores from pre-treatment to following treatment
Video-Perceptual Analysis	Analysis of stroboscopic parameters by expert raters as well as quantification of lesion size
Audio-Perceptual Analysis	The CAPE-V stimuli will be analyzed using a visual analog scale with expert listeners
Aerodynamic Voice Analysis	Collection of acoustic output (dB) and pulmonary pressure (cmH2O) during /pa/

Figure 3. Dependent variables to be analyzed in the current proposal.

Figure 4

[figure not shown]

Figure 4: This image shows the methodology of quantifying lesion size. (A) Representative image of right vocal fold polyp. (B) Lesion area and vocal fold length to be measured. (C) Angle of anterior commissure to be measured.

Name _____

Date _____

I would rate my degree of talkativeness as the following: (circle response)

1	2	3	4	5	6	7
Quiet Listener			Average Talker			Extremely Talkative

FOR STAFF USE	
1- TALK	_____
2- VHI-10	_____
3- RSI	_____
4- SVHI-10	_____

VHI-10 Instructions: These are statements that many people have used to describe their voices and the effects of their voices on their lives. Circle the response that indicates how frequently you have the same experience.

My voice makes it difficult for people to hear me.	0	1	2	3	4
People have difficulty understanding me in a noisy room.	0	1	2	3	4
My voice difficulties restrict personal and social life.	0	1	2	3	4
I feel left out of conversations because of my voice.	0	1	2	3	4
My voice problem causes me to lose income.	0	1	2	3	4
I feel as though I have to strain to produce voice.	0	1	2	3	4
The clarity of my voice is unpredictable.	0	1	2	3	4
My voice problem upsets me.	0	1	2	3	4

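### The edited stroboscopy clips are required to show mucosal wave, which is one of the two features then rated, so changes in its presence or continuity can be masked or lost

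*Combined protocol and SAP*

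**What the plan says.** Item 2 (Video-Perceptual Analysis) of Dependent Variables and Data Collection provides for three recorded exams per subject: initial, interval and final. For the expert rating, each recording is stripped of identifiers and cut down to the portions judged most telling, with this required content: "including clear imaging of the pathology and at least 5 seconds of continuous mucosal wave". The clips are arranged in pairs: "The clips will be paired as follows: initial with interval and interval with final". They go to six outside laryngology experts, and "the reviewers will be asked to rate change in both mucosal wave and glottal closure on a relative 3-point scale", the categories being worse, same and better.

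Figure 3 lists this among the dependent variables: "Analysis of stroboscopic parameters by expert raters as well as quantification of lesion size". Under Sample Size and Statistical Considerations, every variable is compared between arms by a two-tailed t-test, so the wave rating is meant to support an arm comparison.

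The text does not say what happens to an exam without 5 seconds of unbroken wave, who cuts the clips, or which segment is taken when several would qualify. Under Subjects and Protocol, people who collect or analyse data are blinded to drug. The clip editor is not named there, and blinding of the editor to visit is not mentioned.

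**The concern.** What the experts see should not be chosen by reference to what they are asked to judge. Here it is, for one of the two rated features. If a wave is absent throughout an exam, no compliant clip exists. If it comes and goes, the editor is directed to a stretch where it is present, and the experts never see the interruptions.

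The rule covers every clip, so it can act in both directions. A subject who goes from intermittent to steady wave may be rated the same, and so may one who deteriorates from steady to intermittent. At stake is how well one secondary rating can show change, and therefore a difference between arms in that rating.

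**Working it through.** The plan states no figure on this point, so there is none to reproduce. The check is a reading of the text followed by an illustration.

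**1. When the rule binds.**
- Wave continuous at both visits of a pair: both clips comply, and differences in the quality of the wave can be rated.
- Wave intermittent at one visit: a compliant clip may exist, but it shows only an unbroken stretch. The difference in continuity is not visible to the experts.
- Wave absent at one visit: no compliant clip. The text does not say whether the exam is omitted, shown anyway or scored as absent.

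**2. Which comparisons a non-compliant exam touches.** Three exams form two pairs. The initial exam enters one pair, the final exam one, and the interval exam both. If clips were dropped, a failed interval exam would cost both comparisons for that subject, and the glottal-closure rating with them.

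**3. Relation to randomisation.** The initial exam belongs to the visit that precedes enrolment and the opening of the envelope. Its failure is a baseline characteristic, balanced between arms in expectation. Failure of an interval or final exam comes after allocation and could differ by arm.

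**4. Illustration of size.** All inputs here are assumptions; none is in the documents.
- Score worse = −1, same = 0, better = +1.
- True proportions (worse/same/better): steroid 0.10/0.30/0.60, placebo 0.25/0.35/0.40.
- A fraction f of one category is affected, equal in both arms.

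With w and b the proportions worse and better, an arm's mean is b − w. The true difference is (0.60 − 0.10) − (0.40 − 0.25) = 0.50 − 0.15 = 0.35.

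Formulas for an arm's mean:
- worse shown as same: b − (1−f)w
- better shown as same: (1−f)b − w
- worse dropped: [b − (1−f)w] / (1 − fw)
- better dropped: [(1−f)b − w] / (1 − fb)

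At f = 50%:
- worse shown as same: (0.60 − 0.05) − (0.40 − 0.125) = 0.55 − 0.275 = 0.275
- better shown as same: (0.30 − 0.10) − (0.20 − 0.25) = 0.20 + 0.05 = 0.25
- worse dropped: 0.55/0.95 − 0.275/0.875 = 0.579 − 0.314 = 0.265
- better dropped: 0.20/0.70 − (−0.05)/0.80 = 0.286 + 0.0625 = 0.348

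| f | worse shown as same | better shown as same | worse dropped | better dropped |
|---|---|---|---|---|
| 0% | 0.35 | 0.35 | 0.35 | 0.35 |
| 25% | 0.3125 | 0.300 | 0.312 | 0.356 |
| 50% | 0.275 | 0.250 | 0.265 | 0.348 |
| 100% | 0.200 | 0.150 | 0.133 | 0.167 |

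Masking shrinks the difference at every f above zero. Dropping usually does, with one small exception (0.356). The last column needs care. It removes only improved pairs, whereas a failed initial exam would remove its pair whatever happened later. By step 3, that loss narrows the analysed group and costs precision, but does not by itself differ by arm.

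**The case against.** The strongest reply is that the phrase may be a technical minimum: enough uninterrupted stroboscopic footage for an expert to judge. On that reading nothing is selected on the outcome. The text does not settle which was meant, and it refers to earlier work by the group for the rating, which cannot be consulted here. As written, though, the requirement names the wave and not the footage, so the wording needs correcting even if the intent was harmless.

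The second reply is that the rating is relative and both clips of a pair follow the same rule. This stands in part. Differences in wave quality between two compliant clips can still be rated worse or better. Applying the rule equally does not bring back information on presence or continuity.

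The third reply is that people handling data are blinded to drug. This guards against deliberate favouring of an arm if the editor is among them. It does not undo a rule that steers every clip toward visible wave.

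Two stronger readings are tempting and are not supported. A reader might infer that the plan removes subjects or visits with poor outcomes. The sentence concerns de-identifying and shortening a recording and states no exclusion; it also applies to initial clips, so large improvements are as exposed as poor results. A reader might also turn lost clips into lost power using the sample-size assumptions, a difference of 4 (14 against 10) with SD 7. Those figures describe change in VHI-10. The documents give neither an effect size nor an SD for the wave rating, so no power loss can be computed for it.

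**Conclusion.** The concern holds for one of two ratings within one secondary measure. A stated rule conditions the clips on a feature that the experts then rate, and the plan is silent on exams that cannot meet it. Attenuation of the mucosal-wave rating is the likely effect. Its size depends wholly on how many exams lack 5 seconds of unbroken wave, by arm and visit, and the documents do not give this. The illustrated range for masking, from 0.35 down to 0.15, spans no effect to the complete masking of one category. It rests on the assumed rating distributions and on an equal affected fraction in both arms; if that fraction differed by arm, the direction would not be assured.

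It would be wrong to infer that the trial's main result is at risk. Change in VHI-10 does not depend on the clips, and lesion size is measured on open-position stills. Glottal closure is affected only if a clip is dropped. The point is worth acting on because the remedy is cheap, not because the harm has been shown to be large.

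**What to change.** In item 2, replace the wave criterion with one that does not depend on the rated feature. The clip should contain an unbroken run of 5 seconds or more of stroboscopic phonation with the glottis in view, whether or not a mucosal wave is visible. The segment should be taken by a fixed rule, for example the first one that qualifies, by an editor blind to arm and visit. Exams with no visible wave should be shown to the experts and rated, and their number reported by arm and visit.

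The cost is a sentence or two in the editing procedure and a simple count in the report. No extra exam, expert or visit is needed. The downside is that some clips will be less clear than a hand-picked stretch. The change should be made before clips are cut and rated, because change that the experts were never shown cannot be recovered in the analysis of their ratings.

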- 3. Audio-perceptual Analysis.** Auditory perceptual analysis will be performed based on the protocol recently developed as a component of the Consensus Auditory-Perceptual Evaluation of Voice (CAPE-V). Subjects are asked to repeat pre-determined sentences into a microphone. The stimulus sentences are collected as a component of routine clinical care at the NYU Voice Center and archived permanently via the Computerized Speech Laboratory (KayPentax, Montvale, NJ). These digitized files will then be culled, edited, and presented in random fashion to three expert listeners (speech pathologists with particular expertise in voice who are uninvolved in the current experiment). The standardized CAPE-V forms will be employed using

the visual analog scale. Data will be collected via measurement of the hatch mark on the 100mm line for each variable. Twenty (20) percent of the samples will be repeated randomly to assess intra-rater reliability. Data will also be subjected to analysis inter-rater agreement as well as the overall change from pre-therapy to the two treatment arms.

- 4. Aerodynamic Analysis of Voice.** Aerodynamic analysis of voice will be employed to quantify vocal efficiency (i.e., acoustic output as a function of the pulmonary pressure required to sustain phonation). These measurements are collected as a component of routine patient care at the NYU Voice Center using the Phonatory Airflow System (KayPentax, Montvale, NJ). Essentially, patients are instructed on the appropriate positioning and placement of the mask to ensure no air leakage. Patients are then instructed to produce five productions of /pa/ at their most comfortable pitch and loudness at a rate of approximately 1.5 syllables per second. This protocol is followed at least twice to ensure compliance. The middle three productions will then be subjected to analyses, specifically the variables of average phonatory pressure and dB output will be obtained. This protocol has been described extensively in the literature.(31)

Data Analysis.

In general, data analysis will consist of comparisons of the above collected outcome variables measures from initial to interval evaluations and from interval to final evaluations. Where applicable, we will also conduct comparisons between initial and final evaluations.

Research Versus Non-Research Procedures.

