Each data will be analyzed separately and presented descriptively as a mean and standard deviation. Furthermore, each variable will be subjected to independent two-tailed t-tests to determine statistically-significant differences between the two experimental arms. Given the diversity of outcomes and the fact that they are largely independent, there does not appear to be the need to perform a Bonferroni adjustment to avoid Type I error. However, the data will be scrupulously analyzed and if evidence of Type I error is observed, such an adjustment will be made.

Timeline.

It is anticipated that the project will take approximately 12 months to complete. We estimate that recruitment and treatment will take place in 11 months and that there will be a 1-month period of data analysis.

Research Staff.

The following are the research staff for this study and their roles:

[name], Director, NYU Voice Center, Associate Professor, Dept. of Otolaryngology – will perform videostroboscopy and he has expertise in the diagnosis and management of vocal pathology.

[name], Assistant Professor, Dept. of Otolaryngology – will collect voice recordings and aerodynamic measures and has expertise in voice evaluation and conducting voice research.

[name], MA, CCC-SLP, Rusk Institute of Rehabilitation – will provide voice therapy. She is a voice pathologist and specialist in the rehabilitation of the injured voice.

[name] MD, NYU Voice Center – will be the study coordinator. He is a research associate and has expertise in conducting voice related research.

Facilities.

The research will be conducted at the clinical offices of [name] (PI), located at [name] and at Rusk Rehabilitation Outpatients Services, ACC- [name]. The offices have the necessary equipment, personnel, and computer hardware/software for conducting the study.

Limitations.

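### Expert stroboscopy ratings never compare the initial with the final video, so overall change in mucosal wave and glottal closure is not rated and in general cannot be reconstructed

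*Combined protocol and SAP*

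**What the plan says.** Under Dependent Variables and Data Collection, item 2 (Video-Perceptual Analysis), the protocol states: "There will be a total of three videos collected from each subjects (initial, interval, and final"). On review it says "The edited clips will then be sent to 6 expert reviewers", and on pairing, "The clips will be paired as follows: initial with interval and interval with final". For each pair the reviewers are to "rate change in both mucosal wave and glottal closure on a relative 3-point scale (worse, same, better"). No per-visit score is planned for these two parameters, and no rule is given for combining the two relative ratings.

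The Data Analysis section plans comparisons of outcome "measures from initial to interval evaluations and from interval to final evaluations", and adds: "Where applicable, we will also conduct comparisons between initial and final evaluations". It does not say to which outcomes the last sentence applies. Under Sample Size and Statistical Considerations, "each variable will be subjected to independent two-tailed t-tests to determine statistically-significant differences between the two experimental arms". Figure 3 lists the expert-rated stroboscopic parameters among the dependent variables.

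**The concern.** The Specific Aims ask whether steroid before voice therapy gives a better result than voice therapy without it, across objective, subjective and patient-based measures. For an outcome scored at each visit, overall change is a subtraction. The expert ratings have no visit-level value. They exist only as two relative judgements that meet at the interval visit, and a direction without a size does not add up across two steps.

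The interval visit also comes after randomisation and after the drug course. The protocol itself expects the steroid to shrink lesions and improve glottal closure before therapy starts. The starting picture of the interval-final pair may therefore differ between arms because of treatment. A between-arm test on that pair compares progress from unequal starting points, not where subjects end up. Because the initial-interval pair omits therapy, neither planned rating answers the end-of-treatment question for these two parameters.

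**Working it through.** The plan gives no figure to reproduce here. The check is logical, followed by an illustration on assumed inputs.

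**1. What two ratings determine.** Let d1 be the change from initial to interval and d2 the change from interval to final. Assume a reviewer says *better* if d > t, *worse* if d < −t, and *same* otherwise. The overall category depends on d1 + d2.

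| Ratings (in either order where they differ) | Sequences | Range of d1 + d2 | Possible overall category |
|---|---|---|---|
| better, better | 1 | above 2t | better |
| worse, worse | 1 | below −2t | worse |
| better, same | 2 | above 0 | better or same |
| worse, same | 2 | below 0 | worse or same |
| better, worse | 2 | unrestricted | any |
| same, same | 1 | −2t to 2t | any |

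Two of the nine sequences fix the overall category, four fix at most its direction, and three leave it open. If *same* meant exactly zero change, seven of nine would give a direction, and the two better/worse sequences would remain open.

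**2. The post-steroid starting point.** Assumptions, none from the documents: d1 and d2 independent normal with SD 1, t = 0.5, ratings scored −1, 0, +1. Take two arms with the same mean net gain of 1, one gaining early (means 1, then 0) and the other late (0, then 1).

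- Overall change has mean 1 and SD √2 in both arms. The mean overall rating is Φ(0.5/√2) − Φ(−1.5/√2) = 0.638 − 0.144 = 0.49 in each.
- Interval-final, early-gain arm: the change has mean 0, so the mean rating is 0.00 by symmetry.
- Interval-final, late-gain arm: Φ(0.5) − Φ(−1.5) = 0.691 − 0.067 = 0.62.

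Arms with identical overall results thus differ by 0.62 rating points on the only pair that includes the final visit. In the early-gain arm, about 55% of subjects who are truly better overall are rated *same* or *worse* from interval to final (simulation).

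**3. How often the sequence misleads.** Same model, by simulation. The last column takes the sign of the summed ratings as the overall category.

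| Mean changes (d1, d2) | Opposite ratings | Summed rating gives wrong overall category |
|---|---|---|
| 1.5, 1 | 7% | 7% |
| 1, 1 | 9% | 9% |
| 0.5, 0.5 | 16% | 15% |
| 1, 0 | 23% | 19% |
| 1, −1 | 48% | 33% |

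A between-step correlation of +0.5 at means (1, 1) lowers these to 4% and 7%. With t = 1 and SD 1.5 over six other mean patterns, the ranges were 9–40% and 13–27%. These figures are illustrative; they follow the assumed means. The summed rating never reversed the true direction, and the first table shows why: when the sum is positive, d1 + d2 is above 0, and likewise for negative.

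**4. Rating load.** The protocol plans 40 subjects and six reviewers, with this reliability rule: "Twenty (20) percent of the samples will be repeated randomly for both the expert reviewer and lesion measurement analyses". Assume that all 40 complete and that the 20% applies to pairs.

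- Now: 40 × 2 = 80 pairs; × 1.2 = 96 per reviewer; × 6 = 576 pair reviews.
- With a third pair: 40 × 3 = 120; × 1.2 = 144 per reviewer; × 6 = 864 pair reviews.

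**The case against.** The pairing is deliberate and useful. Initial-interval isolates the drug and interval-final isolates the therapy phase, which matches the two main comparisons in the Data Analysis section. This stands, and it is a reason to keep both pairs.

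A reader might infer that the protocol promises an initial-to-final comparison for this outcome and then makes it impossible. The text does not support that. The comparison is planned only where applicable, which can be read as leaving out an outcome with no such pair. The plan is incomplete, because the reader is not told which outcomes are meant, but it does not contradict itself.

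A reader might also infer that overall change can never be derived, or that a steroid subject who improved early must score poorly at the end. Both go too far. Concordant better or worse ratings do fix the overall category, and a subject who improves again during therapy, as the protocol hopes, is rated *better* in both pairs. The error is a possibility whose frequency depends on the course of recovery.

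Finally, the stakes are limited. The primary variable is VHI-10 change from baseline. VHI-10, lesion size, CAPE-V and aerodynamic measures are obtained at all three visits, so their overall change can be computed. The illustration also uses one error-free rater, whereas the plan has six reviewers whose agreement is to be assessed. All of this lowers the weight of the point. None of it supplies an overall rating for mucosal wave or glottal closure.

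**Conclusion.** The point holds as a gap in one secondary outcome. As planned, no pair measures overall change in mucosal wave or glottal closure, and the two phase ratings do not in general recover it: two of nine sequences fix the category under the threshold model. The interval-final rating, used alone, can mislead a between-arm comparison of end results because it starts after the steroid course. In the illustration, equal overall gains gave mean interval-final ratings of 0.00 and 0.62.

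The share of subjects affected cannot be fixed from the documents. With independent steps, the assumed mean changes tried gave about 7–48% opposite ratings and 7–33% wrong overall categories, with no reversal of direction. The logical conclusion does not depend on these figures. The primary analysis is not affected.

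**What to change.** Keep both existing pairs. Add an initial-final pair for each subject, built from the clips already collected and subject to the same random presentation and 20% repeats. In the Data Analysis section, name this rating as the between-arm comparison of overall change in mucosal wave and glottal closure. State that the initial-interval and interval-final ratings describe the drug phase and the therapy phase. Settle this before clips go to the reviewers.

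The cost is 40 more pairs, or 48 more per reviewer with repeats, for the same six reviewers and with no new recordings or visits. Replacing the interval-final pair would avoid the extra ratings, but it would remove a comparison that the Data Analysis section plans, so it is not recommended. If the added load is not acceptable, the protocol should say that these two parameters are analysed by phase only and will not support a conclusion on overall change.
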